4.2.2 Non-Hematologic Dose Limiting Toxicity

Non-hematologic DLT will be defined as any \geq Grade 3 non-hematologic event **with the following exceptions:**

- Grade 3 electrolyte abnormality that lasts less than 72 hours, is not otherwise associated with clinical complications, and responds to medical intervention
- Grade 3 fever that lasts < 72 hours and is not associated with hemodynamic compromise
- Grade 3 nausea or vomiting that lasts < 72 hours and responds to medical intervention
- Grade 3 amylase and/or lipase elevation that is not associated with either clinical or radiographic evidence suggestive of pancreatitis

- Grade 3 gastrointestinal AEs of diarrhea, constipation, abdominal pain, cramping, dyspepsia or dysphagia that resolves to \leq Grade 1 within 14 days with medical therapy
- Grade 3 fatigue that lasts < 7 days
- Grade 3 infusion-related reaction or cytokine release syndrome that lasts < 12 hours and responds to medical intervention.
- Grade 3 or 4 endocrinopathy that is adequately controlled with hormone supplementation
- Grade 3 skin toxicity that resolves to \leq Grade 2 within 14 days of initiation of oral corticosteroids
- Grade 3 inflammatory reaction (e.g., with associated pain, swelling) attributed to a local antitumor response (e.g., inflammatory reaction at sites of metastatic disease, lymph nodes, etc.) that resolves to \leq Grade 2 within 7 days.

Note: The following Grade 2 or greater non-hematologic AE may also be considered as DLT:

- Grade 2 AEs that are prolonged inordinately, based upon the medical judgment of the Investigator, and/or lead to permanent discontinuation of MGA271 due to patient intolerance.
- Any hepatic laboratory abnormalities meeting all three Hy's law criteria (described within **Section 4.2.3** below).
- Any Grade 2 eye pain or reduction in visual acuity that does not respond to topical therapy and does not improve to Grade 1 within 14 days of the initiation of topical therapy, or that requires systemic treatment.

4.2.3 Hepatic Non-Hematologic Dose Limiting Toxicity

- AST or ALT $> 5 \times$ ULN or total bilirubin $> 3 \times$ ULN
 - For patients with liver metastasis who begin treatment with Grade 2 AST or ALT, if the AST or ALT increases by $\geq 50\%$, relative to baseline and lasts for at least 1 week.
 - Please see **Section 6.5.2.2** for further management guidelines.
- Any event meeting the criteria for Hy's law as follows (all three features):
 - Aspartate aminotransferase (AST) and/or alanine aminotransferase (ALT) $> 3 \times$ ULN.
 - Concurrent elevation of total bilirubin $> 2 \times$ ULN without initial evidence of cholestasis.
 - No alternative etiology can be identified.

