- Grade 3 inflammatory reaction (e.g., with associated pain, swelling) attributed to a local antitumor response (e.g., inflammatory reaction at sites of metastatic disease, lymph nodes, etc.) that resolves to \leq Grade 2 within 7 days.

Note: The following Grade 2 or greater non-hematologic AE may also be considered as DLT:

- Grade 2 AEs that are prolonged inordinately, based upon the medical judgment of the Investigator, and/or lead to permanent discontinuation of MGA271 due to patient intolerance
- Any hepatic laboratory abnormalities meeting all three Hy's law criteria (described within hepatic non-hematologic DLTs)
- Any Grade 2 eye pain or reduction in visual acuity that does not respond to topical therapy and does not improve to Grade 1 within 14 days of the initiation of topical therapy, or that requires systemic treatment.

Hepatic Non-Hematologic Dose Limiting Toxicity

- AST or ALT $>$ 5 x ULN or total bilirubin $>$ 3 x ULN

For patients with liver metastasis who begin treatment with Grade 2 AST or ALT, if AST or ALT increases \geq 50%, relative to baseline and lasts for at least 1 week.

Please see [Section 6.5.2.2](#) for further management guidelines.

- Any event meeting the criteria for Hy's law as follows (all three features):

Aspartate aminotransferase (AST) and/or alanine aminotransferase (ALT) $> 3 \times$ ULN

Concurrent elevation of total bilirubin $> 2 \times$ ULN without initial evidence of cholestasis

No alternative etiology can be identified

Dose Escalation Rules

The Dose Escalation Phase of this trial will proceed using a conventional $3 + 3 + 3$ approach, and will begin with enrollment of 3 patients at the initial dose level of 2 mg/kg of pembrolizumab administered as an IV infusion once every three weeks and 3 mg/kg of MGA271 administered as an IV infusion once weekly. Successive dose escalation cohorts will be enrolled as outlined below. The MTD or MAD will be determined based on the assessment of DLTs during the DLT evaluation period. Cohort 4 will begin enrollment of 3 patients at 15 mg/kg MGA271 and 375 mg MGA012; with no higher dose escalation cohorts to be explored.

Patients who do not experience a DLT but are not evaluable for safety for the full DLT evaluation period will be replaced in the same dose-level cohort.

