4.5 Guidelines for Dose Modification

No intra-patient dose escalation will be allowed. No dose reductions will be allowed with exception of 1) reduction of infusion rate during re-challenge for patients experiencing an infusion reaction ([Section 6.5.1](#)) or 2) reduction of dose in patients receiving MGA271 at a dose that is subsequently determined to exceed the MTD ([Section 4.3](#)). For patients who experience DLT that is considered related to either study drug, no further pembrolizumab or MGA271 or MGA012 will be administered.

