 - a. Platelet count $\geq 100 \times 10^3/\mu\text{L}$ without transfusion within 28 days prior to the initiation of study drug.
 - b. Absolute neutrophil count $\geq 1.5 \times 10^3/\mu\text{L}$ in the absence of any growth factor support within 28 days prior to the initiation of study drug.
 - c. ALT/AST $\leq 3.0 \times \text{ULN}$; for patients with hepatic metastases, ALT and AST $\leq 5 \times \text{ULN}$.

- d. Total bilirubin $\leq 1.5 \times$ ULN, except patients with Gilbert's syndrome, who may enroll if the conjugated bilirubin is within normal limits.
- e. Creatinine < 2 mg/dL, or a calculated or measured creatinine clearance > 50 mL/min.

Reproductive Features:

- 11. Female patients of childbearing potential (not surgically sterilized and between menarche and 1 year postmenopause) must have a negative urine pregnancy test performed within 72 hours prior to the initiation of study drug administration. Further, female patients of childbearing potential must agree to either remain abstinent or use acceptable contraceptive measures from the time of consent through 120 days after discontinuation of study drug administration. For female patients, two forms of contraception must be utilized and may include oral, transdermal, injectable or implantable contraceptives, intrauterine device (IUD), female condom, diaphragm with spermicide, cervical cap, use of a condom by the sexual partner or a sterile sexual partner. Periodic abstinence (e.g., calendar, ovulation, symptothermal and postovulation methods) and withdrawal are not considered acceptable forms of contraception in this study.
- 12. Male patients with partners of childbearing potential must use barrier contraception. In addition, male patients should also have their partners use another method of contraception from the time of consent through 120 days after discontinuation of study drug administration.
- 13. Female patients must not be breast-feeding.

Tumor Biopsy

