6.5.2.2 Hepatic Toxicity

6.5.2.2.1 Elevations in Transaminases

Section 2.3.2.1 provides a summary of the pembrolizumab safety profile. Management guidelines for patients experiencing hepatic toxicity are as follows:

Grade 1 elevations

- No specific therapy required

Grade 2 elevations

- For elevations in transaminases 3 to $5 \times$ ULN (Grade 2), rule out viral and other etiologies, consider immediate oral steroids such as prednisone 60 mg /day divided twice daily, and hold MGA271 and pembrolizumab or MGA012.
- If improvement to \leq Grade 1 does not occur within 48 hours with oral steroids, consider IV steroids such as methylprednisolone at 2 mg/kg/day divided twice daily or oral steroids such as prednisone 60 to 120 mg per day, divided twice daily
- Resume pembrolizumab or MGA012, and/or MGA271, at next scheduled dose if:
- No more than one dose of pembrolizumab or MGA012 was missed and no more than 2 doses of MGA271 were missed
- If improvement to \leq Grade 1 does not occur within 14 days discontinue pembrolizumab or MGA012, and MGA271

Grade 3 elevations

- Permanently discontinue MGA271 and pembrolizumab or MGA012, for AST or ALT greater than 5 times ULN unless patient has liver metastasis and began treatment with Grade 2 AST or ALT
- For patients with liver metastasis who begin treatment with Grade 2 AST or ALT, permanently discontinue if AST or ALT increases by greater than or equal to 50% relative to baseline and lasts for at least 1 week
- Initiate IV steroids; suggest methylprednisolone at a dosage of 2 mg/kg/day divided twice daily.
- If no response to corticosteroid therapy within 3 to 5 days is observed, consider adding immune suppression therapy with mycophenolate. Infliximab is not recommended because of a potential for autoimmune hepatitis (30).
- Monitor liver function testing at least twice weekly (or more frequently as clinically appropriate in the judgment of the investigator) until transaminases have returned to Grade 1 or baseline.

Grade 4 elevations

- Discontinue pembrolizumab or MGA012, and MGA271
- Treat as for Grade 3 elevation

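### For liver-metastasis patients who enter with Grade 2 AST/ALT, the protocol's DLT, discontinuation and restart rules do not agree when read literally

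*Protocol*

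**What the plan says.** - **Entry (Section 5.1, criterion 10c).** The usual AST/ALT limit is 3x ULN; "for patients with hepatic metastases, ALT and AST" may be up to 5x ULN. Section 6.5.2.2.1 defines Grade 2 as 3 to 5x ULN, so a patient can be enrolled at Grade 2.
- **General DLT rule (Section 4.2.2).** Any Grade 3 or higher non-hematologic event is a DLT, subject to a list of exceptions. The list has no transaminase item. The section points to 4.2.3 only for Hy's law.
- **Hepatic DLT rule (Section 4.2.3).** The first bullet is "AST or ALT $> 5 \times$ ULN or total bilirubin $> 3 \times$ ULN". Nested under it: "For patients with liver metastasis who begin treatment with Grade 2 AST or ALT, if the AST or ALT increases by" at least 50%, "relative to baseline and lasts for at least 1 week". A cross-reference to Section 6.5.2.2 follows. The synopsis has the same rule in the same place.
- **Management at Grade 3 (Section 6.5.2.2.1).** Both drugs are stopped permanently "for AST or ALT greater than 5 times ULN unless patient has liver metastasis and began treatment with Grade 2 AST or ALT". Those patients stop permanently at a 50% or greater rise over baseline lasting at least 1 week.
- **Management at Grade 2 (same section).** Both drugs are held at 3 to 5x ULN and discontinued if the value does not improve to Grade 1 or lower within 14 days. No baseline exemption is given.
- **Consequences.** After a related DLT, "no further pembrolizumab or MGA271 or MGA012 will be administered" (Section 4.5). After a toxicity that is not a DLT, Section 4.5.1 allows restart once it has resolved to Grade 1 or lower; a drug-related delay of more than 14 days ends both drugs.

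**The concern.** DLT is a primary objective, and the 3+3+3 rules in Section 4.3 act on single events. One disputed event turns 0 of 3 into 1 of 3, which adds three patients, or 2 of 9 into 3 of 9, which declares the MTD exceeded. Two patients with the same DLT among the first six stop the cohort. A laboratory criterion that feeds those counts should give one answer for each patient.

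Here it may not. For one subgroup the protocol has a general rule (4.2.2), a hepatic rule with a nested relative criterion (4.2.3) and a management rule with an explicit exemption (6.5.2.2.1), and does not state which governs. Whether the patient stays on drug also depends on hold and restart rules that take no account of an abnormal entry value.

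**Working it through.** The documents give no figure to reproduce. The check compares the rules and then finds the AST/ALT values at which they diverge. It assumes that the rise is treatment-emergent and judged drug-related, as Section 4.2 requires for a DLT.

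**1. Where the absolute and relative criteria diverge.** Let b be the baseline in multiples of ULN, between 3 and 5. The absolute line is 5; the relative line is 1.5b. A value above 5 and below 1.5b meets only the absolute criterion. That window exists when 1.5b > 5, that is, b > 5/1.5 = 3.33. The rise needed to reach 5x ULN is 5/b − 1.

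| Baseline (x ULN) | Rise that reaches 5x ULN | 1.5 x baseline | Window of disagreement (x ULN) |
|---|---|---|---|
| 3.33 | 50.2% | 4.995 | none |
| 3.5 | 42.9% | 5.25 | 5 to 5.25 |
| 4.0 | 25.0% | 6.0 | 5 to 6.0 |
| 4.5 | 11.1% | 6.75 | 5 to 6.75 |
| 5.0 | 0% | 7.5 | 5 to 7.5 |

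Duration adds a second zone. A rise of 50% or more that exceeds 5x ULN but lasts under 1 week meets the absolute criterion and not the relative one, at any baseline.

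Neither criterion is uniformly the stricter. From 3.1x, a week at 1.5 x 3.1 = 4.65x meets only the relative rule; a brief rise to 5.5x meets only the absolute rule.

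**2. One patient through each section.** Baseline 4.0x, rising to 5.5x: 5.5/4.0 − 1 = 37.5%, which is below 50%.

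- Section 4.2.2: above 5x ULN is Grade 3 by the protocol's own grading in 6.5.2.2.1, with no exception, so a DLT. Section 4.5 then ends all study drug.
- Section 4.2.3, nested criterion replacing the bullet: not a DLT.
- Section 4.2.3, nested criterion adding to the bullet: a DLT.
- Section 6.5.2.2.1, Grade 3 rule: exempt from permanent discontinuation.
- Sections 4.2 and 4.5.1: drug is held during assessment in any case.

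**3. The same patient returns to 4.0x.** The value is back at baseline but is still Grade 2. The Grade 1 condition for restart in 4.5.1 is not met. If that persists beyond 14 days, 4.5.1 ends both drugs, and so does the Grade 2 rule in 6.5.2.2.1. To restart, the patient would need a value below the one at entry. The Grade 3 exemption therefore does not protect a patient who merely recovers to baseline. The Grade 3 monitoring line in 6.5.2.2.1 does accept a return to baseline, so the section is not consistent within itself.

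**The case against.** The strongest reply is that the sections agree once read together. The nested line in 4.2.3 names the same subgroup as 6.5.2.2.1, uses the same 50% and 1-week figures, and is followed by a cross-reference to that part of the protocol. If it only added to the > 5x ULN bullet, it would do nothing for baselines from 3.33 to 5, which is 1.67 of the 2.0-wide Grade 2 range (83%), because a 50% rise there already exceeds 5x ULN. A specific hepatic section would also ordinarily govern over a general one. This largely stands: replacement is the natural reading inside 4.2.3. It does not settle 4.2.2, which has its own list of exceptions, omits transaminases and does not defer.

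A reader might infer more: that the DLT definition has no exception for these patients, or that the management section lets dosing continue through an event that counts as a DLT. The documents support neither. Section 4.2.3 contains a rule for the subgroup, and the exemption in 6.5.2.2.1 lifts only permanent discontinuation; Sections 4.2 and 4.5.1 still hold drug.

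On the Grade 2 rule, it can be said that an unchanged entry value is neither treatment-emergent (Section 7.8.2.4) nor a hepatic toxicity, so the hold would not apply. That is fair for a patient who never moves. It does not help one who rises and returns to baseline, as in step 3.

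Finally, pembrolizumab escalation and expansion are closed with no MTD defined (Section 2.3.1.1.2), and escalation decisions include a full safety review. Both limit the practical effect.

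**Conclusion.** The point holds as a conflict of wording in a narrow subgroup. Read literally, Sections 4.2.2, 4.2.3 and 6.5.2.2.1 can classify the same drug-related transaminase value differently when baseline exceeds 3.33x ULN and the value lies between 5x ULN and 1.5 times baseline, or when a 50% rise above 5x ULN lasts under 1 week. Separately, the Grade 2 management rule and the restart condition in 4.5.1 conflict with inclusion 10c and with the Grade 3 exemption, however 4.2.3 is read.

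The prospective effect on dose decisions is limited to Cohort 4 and its optional de-escalation levels. The documents do not give the number of patients entering with liver metastasis and Grade 2 values, so the frequency of a disputed event cannot be estimated. The SAP does not restate the hepatic criteria and so does not resolve the matter. No view is taken here on which threshold is clinically right.

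**What to change.** Reconcile the synopsis with Sections 4.2.2, 4.2.3, 4.5.1, 5.1 (criterion 10c) and 6.5.2.2.1:

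1. In 4.2.3 and the synopsis, state whether the relative criterion replaces or supplements the > 5x ULN criterion for liver-metastasis patients who enter at Grade 2.
2. State whether 4.2.3 overrides the general rule in 4.2.2 for transaminases, so that one hepatic criterion governs the DLT count.
3. Make the Grade 2, Grade 3 and restart rules treat these patients consistently, including what counts as recovery when the entry value was already Grade 2.

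The clinical team decides which thresholds apply. The cost is protocol wording only: no new data, visits or analyses.

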4.3 Dose Escalation Rules

The Dose Escalation Phase of this trial will proceed using a conventional 3 + 3 + 3 approach, and will begin with enrollment of 3 patients at the initial dose level of 2 mg/kg of pembrolizumab administered as an IV infusion once every three weeks and 3 mg/kg of MGA271 administered as an IV infusion once weekly. Successive dose escalation cohorts will be enrolled as outlined below. The MTD or MAD will be determined based on the assessment of DLTs during the DLT evaluation period. Cohort 4 will begin enrollment of 3 patients at 15 mg/kg MGA271 and 375 mg MGA012; with no higher dose escalation cohorts to be explored.

Patients who do not experience a DLT but are not evaluable for safety for the full DLT evaluation period will be replaced in the same dose-level cohort.

- If 0 of the first 3 patients treated at a given dose level experience a drug-related DLT during the DLT evaluation period, the dose will be escalated and 3 patients will be enrolled and treated at the next higher dose level (up to the planned highest dose level of 15 mg/kg of MGA271).
- If 1 of the first 3 patients treated at a given dose level experiences a drug-related DLT, then 3 additional patients will be enrolled at that dose level (thus making a total of 6 patients in this cohort) to further assess the safety of the combination of MGA271 with pembrolizumab.
- If ≥ 2 of these 3 additional patients (i.e., ≥ 3 of the 6 patients enrolled in the cohort) experience a DLT, it will be concluded that the MTD has been exceeded, and 3 patients will be enrolled and treated at the next lower dose level. If 1 of these 3 additional patients experiences a drug-related DLT, then another 3 additional patients (for a total of 9 patients in the cohort, 3 + 3 + 3) will be enrolled and treated at that dose level to further characterize the safety of the combination. If 0 of the 3 additional patients experiences a DLT, then the dose will be escalated, and 3 patients will be enrolled at the next higher dose level.
- If ≥ 2 patients out of the first 3 patients treated at a given dose level, or ≥ 3 of 6 patients treated at a given dose level, or ≥ 3 out of 9 patients treated at a given dose level experience a drug-related DLT, then it will be concluded that the MTD for MGA271 in combination with pembrolizumab or in combination with MGA271/MGA012 has been exceeded at that dose level, and all subsequent patients will be treated at the next lower dose level.
- If 2 or more patients out of the first 6 patients treated at a given dose level experience **the same** drug-related DLT, then the enrollment in that cohort will stop, and it will be concluded that the MTD for MGA271 / pembrolizumab or MGA271/MGA012 has been exceeded and all subsequent patients will be treated at the next lower dose level.
- Note that in the circumstance in which a DLT occurs during or immediately following the first pembrolizumab or first MGA012 infusion and before the first MGA271 administration, the toxicity will be attributed to pembrolizumab or

MGA012 alone and will not count as a DLT of the combination of study drugs at the dose level under study. In this case the patient will be replaced by another patient in the dose cohort.

Following these rules for dose escalation, the MTD/MAD will be the highest dose administered during the Dose Escalation Phase of the study at which the incidence of DLT is < 33%.

Dose escalation to the next dose level is permitted only after the patients enrolled in the current dose cohort have completed the DLT evaluation period and all safety data have been reviewed by the Sponsor Medical Monitor and the Investigators participating in the study.

For patients being treated at a dose level subsequently determined to exceed the MTD, the dose of MGA271 will be immediately reduced to the next lower MGA271 dose level.

At the discretion of the Sponsor, dose escalation may be stopped before an MTD is reached. In this case, the MAD may be chosen based on an assessment of PK, PD, biomarker, safety, and response data. An MTD does not have to be reached to expand a dose cohort if the available data demonstrate that a lower dose level may provide antitumor activity while minimizing potential risk.

At the discretion of the Sponsor, any escalation cohort at a dose level not exceeding the MTD may be expanded to a maximum of 15 patients for further evaluation of safety and efficacy. For the MGA271 + MGA012(Cohort 4), the cohort may be expanded up to a total of 15 patients.

4.4 Rules for Continuation of Study Therapy

Patients who tolerate treatment with pembrolizumab and MGA271, or who tolerate treatment with MGA271+MGA012, may continue to receive additional treatment with the study drugs as specified in the protocol (see [Section 4.1.1](#)), until any one of the following conditions are met:

- After documentation of a confirmed complete response (cCR), MGA271 and pembrolizumab, or MGA271+MGA012, are continued for one more Tumor Assessment Cycle
- Patient meets criteria for immune-related disease progression (irPD) ([Appendix 6](#))
- Occurrence of drug-related DLT as defined for the DLT Evaluation Period
- The Sponsor, Investigator, or Regulatory Agency terminates the study
- Withdrawal of patient due to an AE or SAE
- Withdrawal of patient consent
- Completion of protocol defined therapy

- Investigator discretion
- Pregnancy
- Death

Note: For individual patients who meet these criteria, but are otherwise considered to be experiencing clinical benefit by the investigator, consideration may be given to extension of therapy on a case-by-case basis in consultation with the Sponsor. If a patient completes 6 cycles of therapy and is experiencing clinical benefit as determined by the investigator, consideration may be given to extension of therapy for an unrestricted number of additional 9-week treatment cycles of MGA271 and pembrolizumab or MGA271+MGA012 on a case-by-case basis in consultation with the Sponsor. Assessments and procedures for Cycles 7 and beyond will be done according to those for Cycle 6 (see [Appendix 1](#)). Such unrestricted treatment may continue until the patient either 1) meets the criteria for permanent discontinuation (see [Section 5.3.1](#)), or 2) a rollover protocol becomes available.

